- a. Does your YNHH privilege delineation currently include the **specific procedure** that you will perform? Yes No
- b. Will you be using any new equipment or equipment that you have not used in the past for this procedure? Yes No
- c. Will a novel approach using existing equipment be applied? Yes No

If you answered "no" to question 4a, or "yes" to question 4b or c, please contact the YNHH Department of Physician Services ([name]) for prior approval before commencing with your research protocol.

IMPORTANT REMINDER ABOUT RESEARCH AT YNHH

Please note that if this protocol includes Yale-New Haven Hospital patients, including patients at the HRU, the Principal Investigator and any co-investigators who are physicians or mid-level practitioners (includes PAs, APRNs, psychologists and speech pathologists) who may have direct patient contact with patients on YNHH premises must have medical staff appointment and appropriate clinical privileges at YNHH. If you are uncertain whether the study personnel meet the criteria, please telephone the Physician Services Department at [contact]. **By submitting this protocol as a PI, you attest that you and any co-investigator who may have patient contact has a medical staff appointment and appropriate clinical privileges at YNHH.**

SECTION I: RESEARCH PLAN

1. **Statement of Purpose:** State the scientific aim(s) of the study, or the hypotheses to be tested.

We propose to examine, in 172 women newly diagnosed with Stage I-III breast cancer who are not practicing the dietary and lifestyle guidelines, and who will receive neoadjuvant or adjuvant chemotherapy as part of their treatment, the effect of a 1-year dietary and physical activity guidelines intervention vs. usual care on the breast cancer outcomes described below. Women will be enrolled either before beginning chemotherapy or following the first chemotherapy infusion but prior to the second chemotherapy infusion (Time 0). Follow up visits will occur post chemotherapy (Time 1), at one-year post-diagnosis (Time 2), at two years post-diagnosis (Time 3) and at five years post-diagnosis.

Primary Endpoints: Adherence to Breast Cancer Treatments

Aim 1a: Chemotherapy completion rates (dose amount, number of dose reductions and dose delays)

Aim 1b: Adherence to endocrine therapy in women taking tamoxifen or Aromatase Inhibitors (AIs) at 12- and 24-months after enrollment

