Lifestyle Interventions and Chemotherapy Completion Rate: Few studies have examined how lifestyle behaviors may impact chemotherapy completion rates. A recent publication by van Waart et al evaluated the effect of a home-based, low-intensity physical activity program (Onco-Move) and a supervised, moderate- to high-intensity, combined resistance and aerobic exercise program (OnTrack) compared to usual care on chemotherapy completion rates (i.e., the percentage of patients who would complete chemotherapy without dose adjustments assessed via medical records)(8) The planned chemotherapy regimens and schedules of the three groups were similar and included combinations of anthracyclines, taxanes, alkylating agents, and antimetabolites. In total, 61 of 230 patients (27%) required chemotherapy dose adjustments, with a smaller percentage of OnTrack participants requiring chemotherapy dose adjustments (12%) than those in the Onco-Move (34%) or usual care group (34%), $p = .002$. The average dose reduction among those who required chemotherapy adjustment in OnTrack and Onco-Move was 10%, compared with 25% in usual care; $P=.014$, with neuropathy being the main reason for dose adjustments.

This study was the first to replicate the previously observed positive effect of exercise on chemotherapy completion rates in Courneya and colleagues' exercise intervention trial in 242 breast cancer survivors initiating adjuvant chemotherapy.(9) Women were randomly assigned to usual care ($n = 82$), supervised resistance exercise ($n = 82$), or supervised aerobic exercise ($n = 78$) for the duration of their chemotherapy (median, 17 weeks; 95% CI, 9 to 24 weeks). While the primary endpoint was quality of life, a secondary endpoint was chemotherapy completion rate. Adjusted mixed-models analyses indicated that resistance exercise was superior to usual care for improving chemotherapy completion rate ($p=.033$). Relative dose-intensity was 84% in the usual care group compared with 90% in the resistance-training group ($P=.033$) and 87% in the aerobic exercise group ($P = .266$). The percentage of

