The MethylationEPIC BeadChip (Illumina; San Diego, CA) will allow us to interrogate >800,000, methylation sites quantitatively across the genome at the Yale Center for Genome Analysis. A sample of pooled female DNA is routinely included on each BeadChip as a control throughout the experiment and assessed for reproducibility using a Pearson R² coefficient. We will set to missing data points with detection p-values >.001 and will exclude any samples with probe detection call rates < 95% as well as those with an average intensity value of either <50% of the experiment-wide sample mean or < 2000 arbitrary units (AU). To limit confounding due to positional effects, samples for each person will be run in the same row.

P16 Human p16 ELISA Kit (LSBio) will be used according to manufacturer's instructions.

***Stool collection:** A stool collection kit, collection and mailing instructions will be provided to each participant to collect a stool sample in their home as baseline, post chemo and 1-year. Stool will be returned by pre-paid Fed Ex delivery to the Yale School of Public Health. Samples will be frozen and then sent for analysis to outside laboratories (Metabolon and [name] at UCSD). Women who are randomized after their first chemotherapy session (but prior to their second session) will not be asked to complete the stool collection at baseline or thereafter as their stool microbiota may have been affected by the chemotherapy so change in microbiota would be uninterpretable.

Analysis of Chemotherapy Completion Rate: Chemotherapy completion rate will be assessed (via medical records in EPIC) as the average relative dose-intensity (RDI) for the originally planned regimen

based on standard formulas. We will measure the number and percent of patients requiring dose-adjustments, who have dose-delays, the reason for the dose-adjustment/dose delays (e.g. neuropathy or vacation) and the percent dose reduction for each participant and by group, similar to Courneya and van Waart's papers.(8, 9) All relevant data will be extracted from EPIC (electronic medical records).

Analysis of Pathologic Complete Response: Pathology reports will be used to evaluate residual tumor after neoadjuvant chemotherapy. Pathologic complete response will be defined as no evidence of viable invasive tumor cells at the primary tumor site and axillary lymph nodes in the surgical specimen, regardless of the presence of non-invasive breast cancer or DCIS (Tis); i.e., yT0/TisN0.

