Relative dose intensity will be calculated using the methods described by Longo et al [24]. The primary endpoint, RDI will be analyzed both as a continuous scale using the t test, and as a dichotomized outcome using 85% or 95% cut-off for Mantel-Haensel chi-square test controlling for stratification factors. In addition, group differences in chemotherapy completion rates will be analyzed with binary logistic regression analysis; whether or not having dose reduction during the period of chemotherapy treatment (the period between T0 and T1) will be the dichotomized dependent variable. The outcome of endocrine therapy adherence will be assessed at the 2 and 5-year follow ups (as most, if not all, participants prescribed endocrine therapy will have been taking it for at least 1 year at the 2-year visit, allowing us to assess adherence to endocrine therapy). The primary endocrine therapy outcome will be adherence to endocrine therapy assessed via the electronic medical records. Note: the assessment for the primary outcome of endocrine therapy adherence was changed from the initial assessment (urinary metabolites) as the COVID pandemic limited our ability to collect urine samples.

Secondary assessments of endocrine therapy will be:

a) Urinary AI level. An undetectable level will classify the participant as nonadherent to AIs.

b) Responses to the following questions:

(1) “In the past month, how often did you take your medications as the doctor prescribed?” Possible responses are all of the time (100%), nearly all of the time (90%), most of the time (75%), about half the time (50%), or less than half the time (<50%). Nonadherence is defined as 75% of the time or less.

(2) “In the past month, how often did you forget to take 1 or more of your prescribed medications?”

Possible responses were never, once in the past month, 2 to 3 times in the past month, once per week, several times per week, and nearly every day. Nonadherence is defined as forgetting to take prescribed medications once per week or more.

(3) “In the past month, how often did you decide to skip 1 or more of your prescribed medications?”

Possible responses were the same as for question 2. Nonadherence is defined as deciding to skip medications once per week or more. The first will be the primary measure of non-adherence. (73,74).

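### The supplementary chemotherapy-completion model counts only dose reductions, so, read literally, a woman who stops early at full dose falls in the favourable category

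*Combined protocol and SAP*

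**What the plan says.** Section I, item 12 (Statistical Analyses) makes RDI the primary chemotherapy outcome: "The primary endpoint, RDI will be analyzed both as a continuous scale using the t test", and also dichotomised at 85% or 95%. It then adds a further model: "In addition, group differences in chemotherapy completion rates will be analyzed with binary logistic regression analysis". The outcome of that model is "whether or not having dose reduction during the period of chemotherapy treatment (the period between T0 and T1) will be the dichotomized dependent variable". T1 is the post-chemotherapy visit. Early discontinuation, omitted cycles and delays are not mentioned in the rule.

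Elsewhere completion is described differently:

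- Item 1, Aim 1a: "Chemotherapy completion rates (dose amount, number of dose reductions and dose delays".
- Item 3(c), Study Assessments, where the measure is defined: "Chemotherapy completion rate will be assessed (via medical records in EPIC) as the average relative dose-intensity (RDI) for the originally planned regimen". The same paragraph adds "We will measure the number and percent of patients requiring dose-adjustments, who have dose-delays", together with the reasons and the percent reduction, by participant and by group, on the pattern of two earlier exercise trials.
- Item 2, Background, for one of those trials: "the percentage of patients who would complete chemotherapy without dose adjustments assessed via medical records".
- Item 12, Power and Sample Size Considerations: a binary comparison of dose adjustment, 18% in the intervention arm against 34% in controls.

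**The concern.** Permanent early stopping is the plainest way not to complete chemotherapy. Under the stated rule a woman who stops at full dose has had no dose reduction, so a model described as comparing completion rates places her with the women who finished. A woman with delays only is placed there too. Because T1 follows the end of chemotherapy, an early stopper also has fewer cycles in which a reduction could be recorded.

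At stake is the meaning of a supporting analysis that carries the name of primary Aim 1a. If the intervention works partly by keeping women on treatment, that part of its effect is invisible here. The model could then understate the benefit and disagree with RDI only because of how the outcome is coded.

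**Working it through.** **The plan's own figures.** For RDI (SD 0.10, difference 0.05, two-sided 0.05), 86 per arm gives 90.3% power by the t test, which agrees with the stated 90%. The binary figure does not reproduce. The plan states 81% power for 18% vs 34% with 86 per arm and 10% of the intervention arm dropping out to usual care. The pooled-variance formula is

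power = Φ{ [ d√n − 1.96√(2p̄(1−p̄)) ] / √(p₁(1−p₁) + p₂(1−p₂)) }

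With d = 0.16, n = 86 and p̄ = 0.26, this is Φ{ (1.484 − 1.216) / 0.610 } = Φ(0.44) = 67.0% before any dilution. Diluting the intervention rate to 0.9 × 18% + 0.1 × 34% = 19.6% gives 56.9%. At 125 per arm, undiluted, it is 82.6%, so the 81% may be left over from the superseded total of 250. That is a separate matter; 67.0% is the baseline used below.

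**What the model sees.** In each arm let t be the proportion with a reduction or an early stop, and s the proportion who stop early with no earlier reduction. The model counts t − s, so

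difference seen = (t_usual − t_int) − (s_usual − s_int).

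**Scenario A.** Take the plan's 34% vs 18% as true non-completion. Every s is an assumption, because the documents give no early-stop rate. All rows use 86 per arm, two-sided 0.05.

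| Full-dose stops, usual / intervention | Model sees, usual / intervention | Odds ratio | Power |
|---|---|---|---|
| 0% / 0% | 34% / 18% | 0.43 | 67.0% |
| 5% / 5% | 29% / 13% | 0.37 | 73.5% |
| 10% / 5% | 24% / 13% | 0.47 | 45.9% |
| 10% / 2% | 24% / 16% | 0.60 | 25.7% |
| 16% / 0% | 18% / 18% | 1.00 | null |
| 20% / 0% | 14% / 18% | 1.35 | reversed |

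For the 10% / 5% row: d = 0.11 and p̄ = 0.185, giving Φ{ (1.020 − 1.076) / 0.544 } = Φ(−0.10) = 45.9%.

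From a 16-point true difference, a null needs s_usual − s_int = 16 points, and a reversal needs more. Equal stopping leaves the 16 points intact.

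**Scenario B.** Suppose instead that 34% vs 18% are reductions alone and full-dose stops come on top. Adding 5% to each arm makes the composite 39% vs 23%. Power is Φ{ (1.484 − 1.282) / 0.644 } = 62.3%, against 67.0% for reductions alone. Adding 10% and 5% makes it 44% vs 23%, with power 83.7%.

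**RDI by contrast.** If cycles not given count as zero against the originally planned regimen, a woman who receives 3 of 4 cycles at full dose has received 3/4 = 0.75 of her planned dose. The primary measure should therefore register the event that the binary model misses.

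**The case against.** The strongest reply is that the coding is inferred. The term dose reduction is not defined. The percent reduction planned for each participant under Study Assessments could be read as total dose received against total planned, in which case an early stopper does have a reduction. The plan also models its measures on two earlier papers that cannot be consulted here. This reading cannot be excluded, but no section states it. Aim 1a, the Columbia recruitment text, the assessment table, the Study Assessments paragraph and the data-collection text in Section IV all list reductions as one item beside delays. For endocrine therapy the plan does write the corresponding rule: reported discontinuation is classified as non-adherence. Chemotherapy has no counterpart.

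The second reply is that the model is supplementary. That stands. The logistic model is additional to RDI, and the sample size of 172 rests on RDI. A reader might infer that the primary conclusion is biased; the documents do not support this, because RDI is taken against the originally planned regimen.

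A reader might also infer that the arm comparison is liable to come out null or reversed. That is arithmetically possible, but from 34% vs 18% it needs an excess of full-dose stops in usual care of 16 points or more. The documents give no stopping rate that would make this expected.

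Finally, the plan already promises adjustments, delays and reasons by group. That is so; only early stopping is not named.

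**Conclusion.** The point holds for the supplementary logistic model. Its stated outcome does not measure completion and disagrees with four other places in the document. Taken as written, it puts full-dose early stoppers in the favourable category. The primary RDI analyses are not shown to be affected.

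The likely effect, if the intervention helps women stay on treatment, is attenuation: 34% vs 18% is seen as 24% vs 13% under assumed full-dose stops of 10% vs 5%, with power at 86 per arm falling from 67% to 46%. The size depends wholly on the assumed stopping rates and on taking the plan's adjustment rates as true non-completion. The finding also rests on the literal reading of dose reduction; if the sponsor means the term to include stopping, the defect is an undefined term and the same sentence of text cures it.

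**What to change.** In item 12, define the binary outcome against the originally planned regimen: non-completion is any dose reduction, any omitted planned cycle, or permanent early discontinuation. State explicitly whether delays count. The plan gives vacation as a possible reason for a dose adjustment or delay, so reporting delays separately is acceptable provided it is stated. Report reduction, delay and early stop by arm. Align the wording in Aim 1a, the Study Assessments paragraph, the Statistical Analyses text and the power text. No separate change to the T0–T1 window is needed once early stopping is itself an event.

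The cost is a small amount of recoding. The plan already abstracts evidence of chemotherapy completion from the medical record, and RDI needs planned and delivered dose, so no new type of data appears necessary. Power falls slightly if early stopping is equal in the two arms (62% against 67% in Scenario B with 5% in each). The change should be made before this model is run. The consent-waiver text shows that some participants were already off study when later analyses were added, so if the model has been run, date the change and report both codings.

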participants who received at least 85% of their planned dose-intensity was 66% in the usual care group compared with 78% in the resistance training group ($P = .082$) and 74% in the aerobic exercise group ($P = .241$). Given the exploratory nature of these findings, they should be replicated before the findings are considered reliable. Neither trial included a diet component in their intervention, thus the combined role of following the dietary and physical activity guidelines on chemotherapy completion rates is unknown.

Adherence to Endocrine Therapy: Approximately 70% of all breast cancers are hormone receptor-positive and are amenable to treatment with adjuvant endocrine therapy (tamoxifen or AIs).(7) Current breast cancer guidelines recommend premenopausal women diagnosed with hormone receptor-positive breast cancer take tamoxifen for 5 years, and recommend postmenopausal women diagnosed with hormone receptor-positive stage I-III breast cancer take an aromatase inhibitor (AI) for 5 years or switch to an AI after two to five years of tamoxifen.(10) However, side effects of tamoxifen and AIs have resulted in poor adherence and discontinuation of the drugs. (10, 11) Factors associated with non-adherence to endocrine therapy include low recurrence risk perception, age, medication cost, low socioeconomic status, suboptimal patient-physician communication, higher comorbidity, cigarette smoking, lack of social support and lower quality of life. (11-13) Primarily as a result of side effects, up to 50% of patients do not adhere to endocrine therapy as prescribed, and 20% discontinue therapy within the first years of use.(11, 12) Both non-adherence and early discontinuation of AIs have been shown to be independent predictors of mortality. (14)

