1. "In the past month, how often did you take your medications as the doctor prescribed?" Possible responses are all of the time (100%), nearly all of the time (90%), most of the time (75%), about half the time (50%), or less than half the time (<50%). Nonadherence is defined as 75% of the time or less.
2. "In the past month, how often did you forget to take 1 or more of your prescribed medications?" Possible responses were never, once in the past month, 2 to 3 times in the past month, once per week, several times per week, and nearly every day. Nonadherence is defined as forgetting to take prescribed medications once per week or more.
3. "In the past month, how often did you decide to skip 1 or more of your prescribed medications?" Possible responses were the same as for question 2. Nonadherence is defined as deciding to skip medications once per week or more. The first will be the primary measure of non-adherence. (73,74) (75) If women switch AIs or from AI to tamoxifen, we will capture this, but classify them as having continued endocrine therapy and therefore adherent. All women who discontinue tamoxifen or AI will

be asked to indicate their rationale(s) via an interview-administered questionnaire. Note: The self-reported adherence questionnaire will be completed independent of whether a urine sample is collected.

Beliefs about Medication Questionnaire: Participants will complete the Beliefs about Medication questionnaire at baseline, 1 2 and 5 years. (78) We will also collect additional information about factors potentially influencing adherence at those 3 time points including: out-of-pocket costs, number and type of other prescriptions (from EPIC), degree to which the patient believes in the drug's efficacy, recurrence risk perception, and social support. These factors as well as age, education, smoking, comorbidities, chemotherapy, and any endocrine therapy side effects they experience during the trial will be examined in relation to endocrine therapy adherence.

COVID-19 Questionnaire

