Participants who report that they have discontinued taking tamoxifen or AI will also be classified as nonadherent to endocrine therapy. For patients who may be lost to follow-up, we will obtain prescription refill data as an endpoint of adherence to endocrine therapy. For the endocrine

therapy aim, we will compare the crude adherence rates using simple logistic regression. Multivariate logistic regression will serve as supportive analyses including covariate adjustments – which are similar to the primary analysis above.

The secondary aims will be performed using Mixed Model Repeated Measures analysis incorporating Analysis of Covariance, where each woman's changes in outcome (follow-up measure – baseline) will be modeled as a function of treatment and time with a covariate included for the baseline value. Prior to fitting models, we will perform exploratory data analyses focusing on the distributions of biological markers by time and intervention group, assessing the appropriateness of log-transformation.

All hypotheses will be tested according to the intention-to-treat philosophy in which all randomized participants will be grouped according to their intervention assignment at randomization, regardless of compliance or adherence to the study. Statistical significance will be defined as $p < 0.05$, 2-sided. Since we have multiple outcomes, we will consider using a Bonferroni correction.

Age, menopausal status, race/ethnicity, BMI at diagnosis, disease stage, type of surgery, type of chemotherapy, radiation therapy, hormone receptor status, endocrine therapy, reconstructive surgery, type 2 diabetes, and smoking status will be examined as covariates. We will explore effect modification by menopausal status at diagnosis, hormone receptor status, and endocrine therapy.

We will further explore intervention effects on study endpoints by stratifying by adherence to diet and physical activity guidelines with a four-level category (e.g., met diet recommendations, met physical activity, met both diet and physical activity recommendations, or met neither recommendation). This analysis will allow us to better understand the role of diet vs. exercise on study endpoints.

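### Read literally, the endocrine adherence rules score a move from tamoxifen to an aromatase inhibitor as nonadherence, because the switch exemption omits that direction

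*Combined protocol and SAP*

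**What the plan says.** Four places in the combined protocol and SAP bear on this.

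- **Section I, item 12, Statistical Analyses, discontinuation rule.** After the list of secondary adherence assessments: "Participants who report that they have discontinued taking tamoxifen or AI will also be classified as nonadherent to endocrine therapy". Nothing there says what happens if another endocrine agent is started.
- **Section I, item 3(c), Adherence to Endocrine Therapy, switch rule.** "If women switch AIs or from AI to tamoxifen, we will capture this, but classify them as having continued endocrine therapy and therefore adherent". The next sentence provides for an interview on the reasons when a woman discontinues. The switch rule is not repeated in item 12.
- **Section I, item 2, Background, Adherence to Endocrine Therapy.** Guidelines are described as recommending that postmenopausal women "take an aromatase inhibitor (AI) for 5 years or switch to an AI after two to five years of tamoxifen".
- **Section I, item 12, measures and timing.** "The outcome of endocrine therapy adherence will be assessed at the 2 and 5-year follow ups". The source of the main measure was changed: "The primary endocrine therapy outcome will be adherence to endocrine therapy assessed via the electronic medical records". No definition of adherent or nonadherent is given for that measure. The secondary measures are urinary AI ("An undetectable level will classify the participant as nonadherent to AIs") and three self-report questions. For the first of these, "Nonadherence is defined as 75% of the time or less".

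**The concern.** Aim 1b, listed under the primary endpoints, asks whether the intervention helps women stay on the endocrine therapy they are prescribed. A woman who took tamoxifen as prescribed and was then moved to an AI has stayed on therapy. If she truthfully reports that she stopped tamoxifen, the item 12 sentence can be applied to her as it stands, and the item 3(c) exemption does not list her case. A woman who moved the other way is expressly adherent. Tamoxifen starters and AI starters could then be scored by different standards, and part of the recorded nonadherence would be a prescribing decision.

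At the least, two analysts could classify the same woman differently. An analyst working from item 12 alone would see no protection for a switch in any direction.

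**Working it through.** **1. Two readings of the discontinuation sentence.** Under reading A, tamoxifen or AI names the drug class, so the sentence means stopping endocrine therapy altogether. Under reading B, stopping either agent is enough. The sentence does not choose between them.

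| Case | Item 3(c) switch rule | Item 12, reading A | Item 12, reading B |
|---|---|---|---|
| AI to tamoxifen | adherent | not a discontinuation | nonadherent, in conflict with 3(c) |
| Tamoxifen to AI | not listed | not a discontinuation | nonadherent, and nothing in 3(c) corrects it |
| Stops all agents | not a switch | nonadherent | nonadherent |

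Only the tamoxifen-to-AI row depends wholly on the reading chosen. It is also the one switch that the Background describes as recommended.

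**2. Which measures are touched.** The sentence concerns what participants report and follows the secondary assessments. The label is broad (endocrine therapy), whereas the urine rule is limited to AIs. A woman now taking an AI would be expected to have detectable urinary AI, and the first self-report question asks about medicines as prescribed, so neither measure penalises her. The medical-record measure has no switch rule in either direction.

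**3. Timing.** The Background places the switch after two to five years of tamoxifen. The 2-year visit is two years after diagnosis, and item 12 expects at least one year on endocrine therapy by then. Chemotherapy takes about 3 to 5 months (item 3, Usual Care Group). If endocrine therapy follows it (assumption), at most 24 − 3 = 21 or 24 − 5 = 19 months of tamoxifen are possible at that visit, short of two years. At the 5-year follow-up the limits are 60 − 3 = 57 and 60 − 5 = 55 months, well inside the switching period. The exposure is therefore mainly at 5 years.

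**4. Size.** The plan's own figure comes first: 50% vs 75%, two-sided 0.05, 90% power, 76 per group (item 12, Power and Sample Size Considerations). With pooled variance,

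n = [1.960 √(2 × 0.625 × 0.375) + 1.282 √(0.50 × 0.50 + 0.75 × 0.25)]² / 0.25² = (1.342 + 0.848)² / 0.0625 = 76.7,

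so 77 per group, and power at 76 is 89.7%. The plan's figure reproduces. With the expected 120 women on endocrine therapy (70% of 172), or 60 per arm, power is 81.6%. That shortfall from 90% comes from having 120 women instead of 152 and has nothing to do with switching.

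Now suppose, purely as an illustration, that a share s of truly adherent women in both arms is mis-scored. The rates become 0.50(1 − s) and 0.75(1 − s).

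| s (assumed) | Rates | Difference | Power at 60 per arm |
|---|---|---|---|
| 0 | 50.0% vs 75.0% | 25.0 points | 81.6% |
| 2% | 49.0% vs 73.5% | 24.5 points | 79.4% |
| 5% | 47.5% vs 71.25% | 23.75 points | 76.1% |
| 10% | 45.0% vs 67.5% | 22.5 points | 70.5% |
| 20% | 40.0% vs 60.0% | 20.0 points | 59.3% |

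Only women who start on tamoxifen can be affected, so s = (share starting tamoxifen) × (share of those who switch and are mis-scored). If half start on tamoxifen (assumption), s = 20% needs 0.20 / 0.50 = 40% of them to be mis-scored, and s = 5% needs 10%. The documents give neither share, so no row of the table is an estimate for this trial.

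**The case against.** The best case for the plan is that reading A is what was meant. The protocol uses tamoxifen and AIs together as its description of endocrine therapy, in Aim 1b and in the Background. Item 3(c) treats a switch as continued therapy and then deals with discontinuation as a separate matter. Reading B would also make AI-to-tamoxifen switchers nonadherent, against item 3(c). On this view the gap is an incomplete list. That is a fair account of the likely intent, but it does not close the gap: the exemption is written as a list, the list omits this direction, and item 12 does not carry it.

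Three stronger conclusions are tempting, and the documents do not support them.

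- *A reader might infer that the plan scores guideline care as failure on a primary endpoint.* No sentence says so. The discontinuation rule rests on participants' reports and follows the secondary assessments, and the primary medical-record measure has no stated switch rule.
- *A reader might infer a material loss of power.* The arithmetic is sound, but the switch rates are assumed, and the planning rates belong to an aim whose primary measure is now the medical record.
- *A reader might infer that any woman taking some endocrine agent should count as adherent, and that stops ordered by the oncologist should be excused.* The first would override the 75%-or-less threshold and turn adherence into persistence. The second is a choice of estimand: the Background attributes nonadherence mainly to side effects, so excusing stops for toxicity could remove part of what the intervention might change.

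**Conclusion.** The concern holds in a limited form. Taken literally, the item 12 sentence and the item 3(c) exemption together make a tamoxifen-to-AI switcher nonadherent to endocrine therapy, while the Background describes that switch as guideline care. Item 12 also leaves out the exemption altogether. The passages must be reconciled.

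The exposure is mainly at the 5-year follow-up, on the assumption that endocrine therapy follows chemotherapy and that switches keep to the timing in the Background. Its size cannot be derived from the documents, and no power loss should be claimed. For the primary medical-record measure, what can be said is that its handling of switches is unstated.

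**What to change.** In item 12, beside the discontinuation sentence, add a rule along these lines:

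> A change from one endocrine agent to another, in either direction between tamoxifen and an AI or between AIs, counts as continued endocrine therapy and is not a discontinuation. The discontinuation rule applies only to women who have stopped all endocrine therapy. The same rule applies to adherence assessed from the electronic medical record.

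Add tamoxifen to AI to the list in item 3(c) so that the two places agree. Leave the self-report thresholds unchanged, since the new rule governs only switches and stops.

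Reasons for stopping are already collected by interview (item 3(c)), so stops ordered by the oncologist can be reported descriptively by arm without changing how they are classified. The type of endocrine therapy and its start date are already abstracted from the medical record. The cost is a few sentences and no new data.
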